4.2.1.1 Reference Glucose Measurements for Endpoint

The primary instrument for plasma glucose measurements is a YSI glucose analyzer (2300 Stat Plus Glucose & Lactate Analyzer, Yellow Springs Instruments, Yellow Springs, OH, USA). Glucose measurements may be re-run on blood samples (replicate measurements). In the event of loss of IV access or loss of functional YSI and need for continued subject monitoring, glucose measurements will be made on capillary whole blood using the Subject SMBG meter as needed.

4.2.2 Safety Endpoint

The safety endpoint is the incidence of device -related or insertion/removal procedure related serious adverse events (SAEs) in the clinic and during home use through 90 days post insertion.

An Adverse Event is considered 'related' if the relatedness is categorized as 'possibly related' or 'related'. The assessment of seriousness and relatedness made by the Medical Monitor will be used for analysis. Only descriptive analysis will be performed for safety endpoints. There is no safety hypothesis.

Other safety endpoints include:

1. Incidence of insertion/removal procedure or device-related adverse events in the clinic and during home use.
2. Incidence of all adverse events in the clinic and during home use.
3. Incidence of hospitalizations due to hypoglycemia, hyperglycemia or ketoacidosis occurring during home use.
4. Incidence of reported hypoglycemic and hyperglycemic events occurring during home use.

4.2.2.1 Safety Assessments

Safety will be evaluated by examination of the insertion site at each in-clinic visit and documentation of adverse events occurring in the clinic and during home use.

At each visit, adverse events that occur during the visit and that occurred during home use since the previous visit will be recorded and reported. Subjects will be asked to provide information on any hospitalizations that may have occurred due to hypoglycemia or hyperglycemia events. Information from the self-monitoring blood glucose meter will be downloaded at each in-clinic visit and used to document episodes of hypoglycemia and hyperglycemia.

4.2.3 Exploratory Effectiveness Endpoints

The exploratory effectiveness endpoints will also be calculated under the same three different configurations of hardware and firmware as noted for the effectiveness endpoint in section 4.2.1. The other effectiveness endpoints include the following.

- System agreement with reference
- Effectiveness measures in full glucose range and different glycemic regions
- Concurrence of System Readings and YSI values
- Stability of the system throughout sensor life
- Sensor precision analysis
- Effect of compression on sensor performance during sleep challenges
- Mean Absolute Difference (MAD) between sensor and reference measurements
- Mean Relative Difference (RD) between sensor and reference measurements
- Median Absolute Relative Difference (ARD) between sensor and reference measurements
- Median Absolute Difference between sensor and reference measurements
- Median Relative Difference between sensor and reference measurements
- Clarke Error Grid Analysis
- Consensus Error Grid Analysis
- Detection and True Alert Analysis
- Deming Regression
- Bland Altman Analysis
- Sensor Survival
- CGM Satisfaction Scale analysis

- Effect of medications
- Calibration Stability

Details of the exploratory effectiveness endpoints are described in Section 6.10.

4.3 Randomization

Subjects will not be randomized. Subjects will be selected consecutively (i.e., selecting every subject in the order they present at the site) among those who meet the inclusion/exclusion criteria.

4.4 Sample Size Determination

Approximately 44 subjects will be enrolled and 36 subjects will be inserted with either one Sensor (dexamethasone sub-group of 6 to 9 subjects) or two Sensors in the clinical investigation. The sample size is not based on any power analysis but was agreed upon by the FDA to satisfy FDA's request for additional data to assess accuracy at different time points through day 30 and to obtain additional plasma levels of dexamethasone using a limit of detection of 50 pg/ml.

5 PROTOCOL

Additional details on the PRECISION protocol not described above can be found in Protocol CTP-0031.

5.1 Schedule of Events

The Schedule of Events for In-Clinic Visits is included below in **Table 1**.

Table 1: Schedule of Events for In-Clinic Visits

Visit Number	1	2	3	4	5	6	7	8	9
Visit Type	Screening	Sensor Insertion and Training	Accuracy Visit	Accuracy Visit	Accuracy Visit	Accuracy Visit	Accuracy Visit	Accuracy Visit and Sensor Removal	Follow-up Sensor Site Assessment
Study Day and Window		Day 0 (+0 to 30 Days after Visit 1)	Day 1 (±0 Day)	Day 7 (± 1 Days)	Day 14 (±1 Days)	Day 30 (±7 Days)	Day 60 (±7 Days)	Day 90 (-3/+7 days)	10 Days Following Sensor Removal (-3/+7 days)
Anticipated Length of Visit	2 Hours	2 to 6 Hours	19 Hours	18 Hours	18 Hours	14 hours	14 hours	15 hours	30 Minutes
Informed Consent Process	X								
Screening history, exam, labs to assess Inclusion/Exclusion	X								
Sensor Insertion		X							
Device Training		X							
Urine pregnancy	X	X	X	X	X	X	X	X	
IV Catheter			X	X	X	X	X	X	
Approximate length of time to collect blood Samples			16 Hours	16 Hours	16 Hours	12.5 Hours	12.5 Hours	12.5 Hours	
Dexamethasone blood draw (4.0 mL) ²	X	X	X ³	X ³	X ³	X	X	X	
HCT	X		X	X	X	X	X	X	
A1C (2.0 mL)	X					X	X	X	
Fingerstick blood glucose and ketones per protocol			X	X	X	X	X	X	

Visit Number	1	2	3	4	5	6	7	8	9
Download Transmitter and BG Meters			X	X	X	X	X	X	
Assess changes in medications and Adverse Events		X	X	X	X	X	X	X	X
Assess Sensor site			X	X	X	X	X	X	X
Hypoglycemia and Hyperglycemia Challenge			X	X	X	X ¹	X ¹	X ¹	
Sleep Assessment				X	X				
Sensor Removal								X	
Approximate Samples for glucose analysis			89 (13 hrs @4 per, 3 hrs @ 12 per)	89 (13 hrs @4 per), 3 hrs @ 12 per	89 (13 hrs @4 per), 3 hrs @ 12 per	59 (11.5 hrs @4 per), 1 hr @ 12 per	59 (11.5 hrs @4 per), 1 hr @ 12 per	59 (11.5 hrs @4 per), 1 hr @ 12 per	
Maximum Estimated Blood Draw Volume ⁴	6	12	97	97	97	65	65	65	Total=504

1 Only hypoglycemia challenge or hyperglycemia challenge, depending on glucose level

2 Designated subjects will have 3 samples drawn at visit 2. A subset of subjects will have daily blood samples drawn for the first 7 days of sensor wear for dexamethasone assessment. Remaining subjects may have an additional blood sample drawn during the first 7 days TBD based on the results from the subset.

3 Subjects will have 2 blood samples drawn for dexamethasone assessment, one at the beginning of the visit, and one at the end.

6 STATISTICAL ANALYSIS

This trial will assess the performance of the Senseonics Continuous Glucose Monitoring System (Senseonics CGM System) when compared to the reference standard (YSI glucose analyzer). The trial has a prospective, single-arm and multi-center design. Approximately 44 subjects with diabetes mellitus will be enrolled in the study. Subjects will be followed for 90 + 10 days following Sensor insertion for safety and effectiveness assessments. The accuracy evaluation period will be from the time of the first valid glucose measurement after Sensor insertion until the Sensor end of life or 90 days post-insertion, whichever occurs first.

6.1 General Considerations

Descriptive statistics will be used to summarize all subject Baseline and outcome data collected during the study. Continuous variables will be summarized using mean, standard deviations, and ranges. Categorical variables will be summarized in frequency distributions.

Statistical analyses will be performed by validated software (e.g., MATLAB, SAS® 9.4 Software). Adequate source document verification and/or audit activities will be utilized to assess the validity of investigation conclusions.

Copies of databases used to prepare clinical report summaries will be archived to enable any statistical analyses performed to be replicated.

6.2 Accuracy Evaluation Period and End of Life

The Senseonics CGM System performance will be evaluated in the period after insertion. The Transmitter will assess the Sensor's signal sensitivity in real time for any premature failure independent of the expected lifetime based on time from insertion. If the measurement of potential degraded response of the Sensor optical system signal drops below a pre-defined percent of its original value and/or systemic patterns in Sensor accuracy to entered calibration points drops below a pre-defined threshold, then the device has reached its end of life and will no longer provide glucose readings. This end of life determination marks the end of the accuracy evaluation period for this Sensor. The distribution of times between Sensor insertion and end of life or 90 days, whichever occurs first will be summarized.

6.3 Data for Analysis

All data will be used for the study safety and effectiveness analysis.

6.4 Analysis Populations

Effectiveness Analysis population: The effectiveness analysis and exploratory effectiveness endpoints will be based on all data from all subjects in this investigation with at least one paired glucose reading (one Sensor with one reference glucose). The Senseonics CGM System and reference readings are compared by pairing each reference reading with the first Sensor reading that occurred up to 5 minutes after sample acquisition.

Safety Analysis Population: Safety analysis will be based on all subjects that undergo the sensor insertion in this investigation.

Dexamethasone Analysis Population: The approximately 6 to 9 subjects with Sensor's inserted will constitute the dexamethasone analysis population to determine if and when a peak dexamethasone level occurs. Subsequent to determining if and when a peak occurs, all subjects with Sensor's inserted will constitute the complete dexamethasone analysis population.

6.5 Dexamethasone Analysis

The peak dexamethasone and the timing that the peak dexamethasone occurs will be analyzed descriptively in the subset of approximately 6 to 9 subjects. Subsequent analysis of the dexamethasone levels in all subjects will be analyzed descriptively.

6.6 Interim Analysis

A planned interim analysis will be performed after all the subjects have completed Visit 6 (day 30 accuracy visit). Only descriptive statistics will be performed. This interim analysis does not feature any stopping rules and has no impact on the collection of the complete follow-up data through 90 days of Sensor use.

6.7 Tabulation of Investigational Device Deficiencies

6.7.1 Transmitter Deficiencies

A tabulation of all reported transmitter device deficiencies will be presented (Table 1 in APPENDIX 1).

6.7.2 Sensor Deficiencies

A tabulation of all reported sensor device deficiencies will be presented (Table 2 in APPENDIX 1).

6.8 Safety Endpoints

The safety endpoint is the incidence of device-related or insertion/removal procedure-related serious adverse events (SAEs) in the clinic and during home use through 90 days post-insertion.

An Adverse Event is considered 'related' if the relatedness is categorized as 'possibly related', 'or 'related'. The assessment of seriousness and relatedness made by the Medical Monitor will be used for analysis. The numbers of SAEs and the percentage of patients with SAEs will be reported for each SAE type that is observed, identified as device-related, procedure-related or unrelated to the study (Table 3 in APPENDIX 1). The count and proportion of patients experiencing at least one device-related or procedure-related SAE will be presented. No inferential statistical analysis will be performed.

Other safety endpoints include:

- Incidence of insertion/removal procedure or device-related adverse events in the clinic and during home use.
- Incidence of all adverse events in the clinic and during home use.
- Incidence of hospitalizations due to hypoglycemia, hyperglycemia or ketoacidosis occurring during home use.
- Incidence of reported hypoglycemic and hyperglycemic events occurring during home use.

For each of the adverse event (AE or SAE) categories above, the numbers of AEs and the percentage of patients with AEs will be reported for each AE type that is observed and be stratified by the target age enrollment categories (Tables 4A-4E in APPENDIX 1). A listing (Table 5 in APPENDIX 1) will be prepared that identifies each patient with a reported AE or SAE, and relevant information including date of onset, severity level, seriousness, relatedness to the device or procedure, classification as anticipated or unanticipated, corrective action(s) taken, and resolution status (resolved or ongoing).

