	
10. Currently receiving (or likely to need during the study period): immunosuppressant therapy; chemotherapy; anticoagulant/antithrombotic therapy (excluding aspirin); glucocorticoids (excluding ophthalmic or nasal). This exclusion does include the use of inhaled glucocorticoids and the use of topical glucocorticoids (over sensor site only); antibiotic for chronic infection (e.g. osteomyelitis, endocarditis)
 
11. A condition requiring or likely to require magnetic resonance imaging (MRI)
 
12. Known topical or local anesthetic allergy
 
13. Known allergy to glucocorticoids
 
14. Any condition that in the investigator's opinion would make the subject unable to complete the study or would make it not in the subject's best interest to participate in the study. Conditions include but are not limited to psychiatric conditions, known current or recent alcohol abuse or drug abuse by subject history, a condition that may increase the risk of induced hypoglycemia or risk related to repeated blood testing. Investigator will supply rationale for exclusion
 
15. Participation in another clinical investigation (drug or device) within 2 weeks prior to screening or intent to participate during the study period
 
16. The presence of any other active implanted device (as defined further in protocol)
 
17. The presence of any other CGM sensor or transmitter located in upper arm (other location is acceptable)

Investigation Objectives	
Effectiveness Objective: To determine accuracy of the Senseonics CGM System measurements through approximately 90 days post-insertion. An interim analysis will be conducted on all subjects after completion of Visit 6 (day 30 accuracy visit).
 
Safety Objective: To demonstrate safety of the Senseonics CGM System through 90 days post-insertion or sensor removal and follow-up by measuring the incidence of device-related and insertion/removal procedure-related serious adverse events during the investigation.

Endpoints	
Effectiveness Endpoint: The effectiveness endpoint will be mean absolute relative difference (MARD) for paired Sensor and reference measurements through 90 days post-insertion for reference glucose values from 40-400 mg/dL. This endpoint will be evaluated descriptively. Neither inferential analysis nor hypothesis testing will be performed. An interim analysis will be conducted on all subjects after completion of Visit 6 (day 30 accuracy visit).

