	
Safety Endpoint: Incidence of device-related or sensor insertion/removal procedure-related serious adverse events through 90 days post-insertion or sensor removal and follow-up.

Other Safety Endpoints	
 1. Incidence of all device-related or sensor insertion/removal procedure-related adverse events in the clinic and during home use. 2. Incidence of all adverse events in the clinic and during home use. 3. Incidence of hospitalizations due to hypoglycemia, hyperglycemia or ketoacidosis occurring during home use. 4. Incidence of reported hypoglycemic and hyperglycemic events occurring during home use.

ABBREVIATIONS

AE	Adverse Event
BG	Blood Glucose
BG Meter	Blood Glucose Meter (also known as SMBG Meter)
β-HOB	β-hydroxybutyrate or “ketones,” also abbreviated B-HOB
BMI	Body Mass Index
CD	Compact disc
CFR	Code of Federal Regulations
CGM	Continuous Glucose Monitoring
CRF	Case Report Form
CRO	Contract Research Organization
DCF	Data Clarification Form
DKA	Diabetic Ketoacidosis
eCRF	Electronic Case Report Form
EKG	Electrocardiogram (also commonly abbreviated as ECG)
FDA	Food and Drug Administration
GCP	Good Clinical Practice
HbA1c	Hemoglobin A1c or A1C
HCT	Hematocrit
HIV	Human Immunodeficiency Virus
HHD	Hand Held Device
ICH	International Conference on Harmonization
IRB	Institutional Review Board
ISO	International Organization for Standardization
MARD	Mean absolute relative difference
MAD	Mean absolute difference
MDI	Multiple Daily Injections
MMA	Mobile Medical Application
MRD	Mean relative difference
PARD	Percent absolute relative difference
PI	Principal Investigator
POC	Point of Care
SAE	Serious Adverse Event
SMBG	Self-Monitoring Blood Glucose
SQ	Subcutaneous
UADE	Unanticipated Adverse Device Effect
USB	Universal Serial Bus
YSI	Yellow Springs International (Blood glucose analyzer)

1	INTRODUCTION, IDENTIFICATION OF THE INVESTIGATIONAL DEVICE, AND RATIONALE	15
1.1	Names, Intended Use, and Description of Study Device	15
1.2	Summary of Pre-clinical and Clinical Experience	18
2	STUDY OBJECTIVES	19
2.1	Effectiveness	19
2.2	Safety	19
3	STUDY DESCRIPTION	19
3.1	Study Population	19
3.2	Inclusion and Exclusion Criteria	19
3.3	Study Design	21
4	STUDY METHODS, PROCEDURES AND CLINIC VISITS	23
4.1	Visit 1 – Screening/Enrollment	25
4.2	Visit 2 – Sensor Insertion/Training	26
4.3	Subset of subjects for dexamethasone analysis	29
4.4	Sensor Accuracy (Sampling) Visit 3 – Day 1 (\pm 0 Days)	29

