2.2 Safety

The safety objective is to demonstrate safety of the Senseonics CGM System through 90 days post-insertion by measuring the incidence of device-related or sensor insertion/removal procedure-related serious adverse events (SAEs) during the investigation. The other safety objectives are to evaluate the incidence of all procedure-related or device-related adverse events (AEs) in clinic and home use, and to evaluate the incidence of all adverse events, regardless of relatedness, in clinic and home use. The safety endpoints and their respective analysis are detailed further in Section 11.2.

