Incidence of device-related or insertion/removal procedure-related serious adverse events over the operating life of the Sensor	0	0 (0.0%)
Incidence of insertion/removal procedure or device-related adverse events in the clinic and during home use	12	11 (15.5%)
Incidence of all adverse events in the clinic and during home use	35	24 (26.6%)
Incidence of hospitalizations due to hypoglycemia, hyperglycemia, or ketoacidosis occurring during home use	0	0 (0.0%)
Incidence of reported hypoglycemic and hyperglycemic events occurring during home use	2	2 (2.8%)

Table 4B. Other Safety Endpoint for Subjects between 18 and 20 Years Old (Sample Data)

Type of Incidence	Number of Incidents	Number (%) of Subjects with Incidents
Incidence of device-related or insertion/removal procedure-related serious adverse events over the operating life of the Sensor	0	0 (0.0%)
Incidence of insertion/removal procedure or device-related adverse events in the clinic and during home use	12	11 (15.5%)
Incidence of all adverse events in the clinic and during home use	35	24 (26.6%)
Incidence of hospitalizations due to hypoglycemia, hyperglycemia, or ketoacidosis occurring during home use	0	0 (0.0%)
Incidence of reported hypoglycemic and hyperglycemic events occurring during home use	2	2 (2.8%)

Table 4C. Safety Endpoint for Subjects between 21 and 44 Years Old (Sample Data)

Type of Incidence	Number of Incidents	Number (%) of Subjects with Incidents
Incidence of device-related or insertion/removal procedure-related serious adverse events over the operating life of the Sensor	0	0 (0.0%)
Incidence of insertion/removal procedure or device-related adverse events in the clinic and during home use	12	11 (15.5%)
Incidence of all adverse events in the clinic and during home use	35	24 (26.6%)

Incidence of hospitalizations due to hypoglycemia, hyperglycemia, or ketoacidosis occurring during home use	0	0 (0.0%)
Incidence of reported hypoglycemic and hyperglycemic events occurring during home use	2	2 (2.8%)

Table 4D. Safety Endpoint for Subjects between 45 and 65 Years Old (Sample Data)

Type of Incidence	Number of Incidents	Number (%) of Subjects with Incidents
Incidence of device-related or insertion/removal procedure-related serious adverse events over the operating life of the Sensor	0	0 (0.0%)
Incidence of insertion/removal procedure or device-related adverse events in the clinic and during home use	12	11 (15.5%)
Incidence of all adverse events in the clinic and during home use	35	24 (26.6%)

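### The main safety endpoint counts removal-procedure SAEs but closes at Day 90, before Visit 9 whenever removal takes place at an on-schedule Visit 8

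*SAP*

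**What the plan says.** **Safety.** SAP 6.8 sets the endpoint as device-related or "insertion/removal procedure-related serious adverse events (SAEs) in the clinic and during home use through 90 days post-insertion". Protocol 11.2 has the same words, and SAP 4.2.2 nearly so ("serious adverse events (SAEs) in the clinic and during home use through 90 days post insertion"). The objective in protocol 2.2, repeated in SAP 4.1.2, is to "demonstrate safety of the Senseonics CGM System through 90 days post-insertion by measuring the incidence" of such events, though that sentence goes on to place the measurement over the whole investigation. The synopsis differs. Its objective is "To demonstrate safety of the Senseonics CGM System through 90 days post-insertion or sensor removal and follow-up" and its endpoint is "serious adverse events through 90 days post-insertion or sensor removal and follow-up". Two looser phrases also bear on the window: SAP 6 says "Subjects will be followed for 90 + 10 days following Sensor insertion for safety and effectiveness assessments", and the Table 4 shells label the endpoint row "insertion/removal procedure-related serious adverse events over the operating life of the Sensor".

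**Calendar.** Visit 8, with removal, is Day 90 with a -3/+7 day window (protocol 3.3.3). Protocol 4.7 allows earlier removal and deferral to Day 100. Protocol 4.8 times Visit 9 from the removal date. Protocol 9.3.1 collects adverse events until participation ends.

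**MARD.** Protocol 11.3.1 and SAP 6.9 base the interim MARD on the 30 days after insertion. Protocol 2.1 and SAP 4.1.1 base the interim submission on data through Visit 6, which has a window of 7 days either side of Day 30. For the final analysis, SAP 6 ends the accuracy period at sensor end of life or Day 90. Sensor life is summarised up to the last planned visit in protocol 11.1.3, but up to Day 90 in SAP 6.2.

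**The concern.** An endpoint that counts removal complications has to stay open long enough to see them. Protocol 8.2.1 lists poor healing after removal, infection, retained fragments, failed retrieval and difficult removal among the anticipated effects. Whichever of these prove serious will arise at or after removal, and Visit 9 exists to examine the healing sites. A programmer who follows the endpoint sections would leave an SAE found at Visit 9 out of the headline figure. One who follows the synopsis could count it.

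The interim MARD raises a similar question on a smaller scale. It supports a data submission, yet its data set could depend on which sentence is followed.

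**Working it through.** **Step 1. Reproduce the Visit 9 window.** Protocol 3.3.3 gives 10 days after removal, -3/+7. So 10 - 3 = 7 and 10 + 7 = 17, which matches the +7 to 17 days in protocol 4.8.

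**Step 2. Place removal and Visit 9 on the calendar.**
- Visit 8: 90 - 3 = Day 87 to 90 + 7 = Day 97.
- Visit 9 after removal at Visit 8: earliest 87 + 7 = Day 94, nominal 90 + 10 = Day 100, latest 97 + 17 = Day 114.
- Visit 9 after removal deferred to Day 100: 107 to 117.
- Seven of the 11 permitted Visit 8 days (91 to 97) put the removal itself past Day 90.

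**Step 3. Post-removal days inside the Day 90 window** = max(0, 90 - removal day).

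| Removal day | Days covered after removal |
|---|---|
| 87 | 3 |
| 88 | 2 |
| 89 | 1 |
| 90 to 100 | 0 |

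The planned follow-up to Visit 9 is 7 to 17 days.

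**Step 4. Early removals.** Visit 9 can fall by Day 90 if removal is by 90 - 7 = Day 83. It always does if removal is by 90 - 17 = Day 73.

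**Step 5. Effect on the headline.** With 36 subjects inserted, one subject whose only related SAE is after Day 90 moves the incidence by 1/36 = 2.8 percentage points.

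**Step 6. Interim MARD.** Inputs are the expected pairs in protocol 11.1.4, based on 66 sensors.
- 16-hour session: 166 + 446 + 1128 + 1078 + 712 + 620 + 290 + 127 + 65 = 4,632.
- 12.5-hour session: 106 + 285 + 722 + 690 + 456 + 397 + 186 + 81 + 42 = 2,965.
- Check: 3 x 4,632 + 3 x 2,965 = 22,791, against the printed 22,786. The gap is consistent with rounding.
- Planned pairs through Visit 6: 3 x 4,632 + 2,965 = 16,861.
- Visit 6 may be held on Days 23 to 37, and 7 of those 15 days are after Day 30.
- Ceiling, every Visit 6 late: 2,965/16,861 = 17.6%.
- Even spread over the window (assumption): 7/15 x 2,965 = 1,384 pairs, and 1,384/16,861 = 8.2%.
- If the Visit 6 MARD differs by d points from that of Visits 3 to 5, including or dropping it moves the interim MARD by at most 0.176 x d.

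**Step 7. Final MARD.** If Day 90 is a calendar limit, a Visit 8 on Days 91 to 97 drops out. The ceiling is 2,965/22,786 = 13.0%. An even spread over the 11-day window (assumption) gives 7/11 x 2,965 = 1,887 pairs, or 8.3%.

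**The case against.** **Safety data after Day 90 are not lost.** A reader might infer that they are. The documents do not support that: collection runs to the end of participation, and late events would appear in the other safety endpoints and the Table 5 listing. This stands, and it confines the point to the headline count.

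**Not every Visit 9 lies outside the window.** That too might be inferred, but protocol 4.7 permits early removal, and Step 4 shows that Visit 9 can then fall by Day 90. The point is limited to removal at or after an on-schedule Visit 8.

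**There are not four established windows.** The SAP 6 sentence describes subject follow-up and equals nominal Day 90 plus the nominal 10 days to Visit 9. The row label sits in shells of sample data whose percentages do not fit this trial: 11 subjects shown as 15.5% implies about 71, and 24 shown as 26.6% implies about 90, not 36. Both are weak evidence of a separate intent. They still need tidying. Read literally, the label could stop the count before removal, because once "the device has reached its end of life and will no longer provide glucose readings" the sensor stays in place until a later visit. The objectives in protocol 2.2 and SAP 4.1.2 are also softer than the endpoint text. The firm conflict is between the synopsis and the endpoint sections.

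**The reporting sentence carries no date limit.** In protocol 11.2 and SAP 6.8, the sentence promising the count and proportion of subjects with a related SAE does not repeat Day 90. It follows a definition that does, so this weakens the strict reading without removing it.

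**Day numbers may be visit names.** Visit 6 is called the day 30 visit, and Table 8 is organised by visit but labelled by day. A reader might infer two truly conflicting interim data sets, but the 30-day wording may simply mean through the Day 30 visit. That leaves an ambiguity, since no passage says which is meant. The same holds for Day 90 in the final MARD, where the cap may also be deliberate given the intended life of up to 90 days.

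**Conclusion.** The safety point holds. As written, protocol 11.2 and SAP 4.2.2 and 6.8 leave out of the headline any removal-related SAE that falls more than 3 days after an on-schedule removal, and all those that follow a removal after Day 90. The synopsis points to a longer window, although its 'or' leaves the end unclear. The size is 2.8 percentage points per affected subject, assuming 36 inserted subjects form the denominator. The documents give no expected number of such events.

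The MARD point is a clarification. Up to 17.6% of interim pairs and 13.0% of final pairs depend on the reading. Those are ceilings that require every Visit 6 or Visit 8 to be late; about 8% is affected in each case under an assumed even spread.

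The study is descriptive, with no hypothesis, threshold or interim stopping rule. This is a matter of aligning the text and does not threaten validity. It should be settled before the interim analysis.

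**What to change.** 1. State one main safety window, through sensor removal and the follow-up visit (Visit 9), in the synopsis, protocol 11.2 and SAP 4.2.2 and 6.8. Align the objectives (protocol 2.2, SAP 4.1.2), the follow-up sentence in SAP 6 and the Table 4 row label.
2. Define the interim MARD in protocol 11.3.1 and SAP 6.9 as all pairs from Visits 3 to 6.
3. State whether Day 90 is a nominal visit or a calendar limit for the final MARD, and align protocol 11.1.3 with SAP 6.2.
4. State whether the day columns of Tables 11A and 11B are nominal visits or calendar days, so that they agree with the MARD. Read as calendar days, a Visit 6 on Days 31 to 37 falls outside the first column, and a Visit 8 on Days 91 to 97 has no column.

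**Cost.** A protocol amendment under protocol 13.4 (sponsor concurrence, IRB and regulatory approval) and a SAP revision recorded in its document history. No new visits or data are needed. The reported SAE incidence may be slightly higher, and a final MARD taken through Visit 8 may include Days 91 to 97, beyond the intended 90-day life.
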